3.4 Previous human [^{18}F]FLT imaging studies

Several preliminary studies using [^{18}F]FLT imaging in human subjects have been performed in Germany and the United States (UCLA, University of Washington in Seattle, Wayne State University)(51-56). The imaging protocols were pre-approved by their respective regulatory committees and conducted under the RDRC process, with patients receiving between 1.4 and 13 mCi of [^{18}F]FLT. Some of the imaging results have been published (**Table 2**). The group in Seattle, which has the most experience with this agent in the US, has performed numerous studies in patients with lung cancer as well as a few in patients with primary brain tumors. Their findings demonstrate the feasibility and merit of tumor imaging with [^{18}F]FLT. [^{18}F]FLT PET showed increased uptake in tumor lesions outside the liver or bone marrow with standardized uptake values (SUV) of 4-7, enabling differentiation from surrounding tissues (SUV 0.5-2).

Table 2 Summary of published manuscripts reporting [¹⁸F]FLT human imaging studies

Year	Organ System	# of pts	mCi injected	MBq Injected	Specific Activity	nmole injected	Reference (#)	Previous Chemotherapy	Time post injection
2006	Brain	10	4	104-202	37-222GBq/umol	N.C.	Yamamoto, 2006 (57)	10 previous chemo	Dynamic 60 min; constant from 10-60min
2006	Lymphoma	34	9.3	265-370	Not reported	N.C.	Buck 2006 (39)	25 none, 9 restaging	60 min
2006	Lung and SPN	22	5	185.2	Not reported	N.C.	Yap, 2006 (58)	none	60 min
2006	Breast	14	4	150	74 TBq/mmol	N.C.	Pio, 2006 (33)	Pre-,after 1-cycle, and post-chemo	Dynamic 45min
2005	Brain	23	8.6	111-370 (321)	Not reported	N.C.	Jacobs,2005 (59)	10 previous chemo	Dynamic 90min
2005	Esophageal	10	11.1	340-450 (410)	>10TBq/mmol	N.C.	van Westreenen, 2005 (60)	None	60 min
2005	Lung	47	9.5	265-370	Not reported	N.C.	Buck 2005 (61)	none	60 min
2005	Breast	10		390-420 (3 patients) 60-250 (7 patients)	>10TBq/mmol	N.C.	Been 2006 (62)	None	3 patients at 30,120,180, and 240 min; others at 120 min
2005	Brain	25	4.7	141-218 (174)	~74 Bq/mmol	N.C.	Chen, 2005 (63)	None	75: 11 patients
									35:13 patients (uptake peaks at 5- 10min)
2005	Brain	26	10	370	0.1-0.3TBq/mmol	N.C.	Choi, 2005 (64)	None	60 min
2004	Lymphoma	7	4.3 - 13.2	Mean = 324	Not reported	N.C.	Buchmann 2004 (65)	Not reported	50-70 min

Year	Organ System	# of pts	mCi injected	MBq Injected	Specific Activity	nmole injected	Reference (#)	Previous Chemotherapy	Time post injection
				159 - 489					
2004	Lung	17	5.7	Mean=210 130-420	>10TBq/mmol =10GBq/umol	40 nmol	Cobben 2004 (66)	None	60 min
2004	Lung	28 (a)	9	Mean=334 265-370	Not reported	N.C.	Halter 2004 (67)	None	80-120min
2004	Breast	12	8.1-12.1	300-450	Not reported	N.C.	Smyczek-Gargya 2004 (68)	None	80-120 min
2004	Colorectal	18	9.7	360 ± 25	Not reported	N.C.	Visvikis 2004 (69)	Not reported	Dynamic 60 min
2004	HEENT	21	9.2	Mean=340 165-650	>10TBq/mmol =10GBq/umol	40 nmol	Cobben 2004 (70)	Not reported	60 min
2004	Soft Tissue	19	10.8	Mean=400 115 -430	>10TBq/mmol =10GBq/umol	40 nmol	Cobben 2004 (71)	Not reported	60 min
2003	Lymphoma	11	7.5	280	Not reported	N.C.	Wagner 2003 (72)	Not reported	60 min
2003	Colorectal	10 (b)	9.5	351 ± 52	Not reported	N.C.	Francis 2003 (73)	Not reported	57+/-10 min
2003	Colorectal	17 (b)	9.4	Mean=360 312-412	Not reported	N.C.	Francis 2003 (74)	Not reported	57-69 min
2003	Dosimetry (Lung)	18	5	185 MBq max	> 37 GBq/umol	5 nmol	Vesselle 2003 (75)	Not reported	2 hour dynamic
2003	Lung	16	5.4 - 10.8	200 - 400	Not reported	N.C.	Dittmann 2003 (76)	None	114+/-20 min

Year	Organ System	# of pts	mCi injected	MBq Injected	Specific Activity	nmole injected	Reference (#)	Previous Chemotherapy	Time post injection
2003	Melanoma	10	10.8	Med= 400 185-430	>10TBq/mmol =10GBq/umol	40nmol	Cobben 2003 (77)	None	60 min
2003	SPN	26 (c)	9	Mean=334 265-370	Not reported	N.C.	Buck 2003 (78)	None	45 min
2002	SPN	30 (c)	9	Mean=334 265-370	Not reported	N.C.	Buck 2002 (79)	None	45 min
2002	Lung	10	5	185 max	1Ci/umol = 37GBq/umol	5 nmol	Vesselle 2002 (80)	None	2-hr dynamic
Total No. Subjects:		380*							

N.C. = not calculated

(a) There appear to be 10 additional unique patients who were not described in the Buck 2002 and 2003 manuscripts.

(b) It is unclear if the same patients are being described for both of the Francis manuscripts.

(c) It is unclear if the same patients are being described for both of the Buck, 2002 and 2003, manuscripts.

* Due to the possibility that the same patients are being described in some reports, the total # of unique patients studied in these published studies appears to be 198.

Version Date: March 08, 2013

Protocol Number(s): CTEP # 8333

CC#: 08-C-0200

As evidenced in [Table 2](#), many of the published studies did not report the specific activity of the [^{18}F]FLT, so it is not possible to determine the amount of FLT that was actually administered to the patient. Furthermore, none of the published studies addressed safety issues by describing laboratory results post injection or assessing for neurological sequelae such as mild peripheral neuropathy.

3.5 Reported Adverse Events and Potential Risks

No adverse events have been reported for [^{18}F]FLT at the dose to be used for this study. As described in [Section 3.2](#), non-radioactive FLT has been investigated as an anti-AIDS drug, and some adverse effects, namely, reversible peripheral neuropathy, were observed in subjects exposed to 50 ng-h/mL plasma over a course of 16 weeks (15 $\mu\text{g/kg}$ q12h). The FLT dose anticipated for this study will be <6.1 μg for a single injection. Assuming a 70kg individual, the maximum concentration of FLT would be expected to be equivalent to 0.29 ng-h/mL. The radiation exposure associated with this study is described in [Section 3.6](#) and is comparable to the dose for other widely used clinical nuclear medicine procedures.

3.6 [^{18}F]FLT Administered Dose

The administered dose will be 0.07 mCi/kg with a maximum of 5 mCi. The drug solution is stored at room temperature in a gray butyl septum sealed, sterile, pyrogen-free glass vial and has an expiration time of 8 hours. The injectable dose of [^{18}F]FLT for most studies will be ≤ 0.07 mCi/kg of fluorine-18, not to exceed 5 mCi with a specific activity greater than 200 Ci/mmol at the time of injection. In the dose of [^{18}F]FLT, only a small fraction of the FLT molecules are radioactive. The amount of injected drug is ≤ 6.1 μg (≤ 25 nmol per dose) of FLT. [^{18}F]FLT is administered to subjects by intravenous injection of ≤ 10 mL. There is no evidence that nonradioactive and radioactive FLT molecules display different biochemical behavior.

3.7 Agent Availability

[^{18}F]FLT will be provided by IBA, or Cardinal Health under an IND held by the Cancer Imaging Program (CIP)/NCI.

4 Eligibility assessment and enrollment

4.1 Eligibility Criteria

4.1.1 Inclusion Criteria

- Participant must be enrolled in a lymphoma therapy study at the NIH Clinical Center OR be enrolled in the CALGB 50303 study at another site OR undergoing a new course of treatment of lymphoma at another facility.
- Participants must have a clinical course consistent with lymphoma and have available documentation of lymphoma from either the NCI or from an outside pathology laboratory.
- Participant must be 18 years or older
- ECOG Performance score of 0 or 1
- Ability to provide informed consent. All patients must sign a document of informed consent indicating their understanding of the investigational nature and risks of the study before any protocol related studies are performed.

For subjects enrolling in early response arm

- Must be enrolled in CALGB 50303 or a lymphoma therapy study at the NIH Clinical Center or undergoing a new course of treatment of lymphoma at another facility

- Must not have begun lymphoma therapy for this tumor occurrence/ relapse
- Prior completed therapy does NOT affect eligibility

For subjects enrolling in the residual FDG avid mass arm

- Must have a residual FDG PET positive mass ≥ 1 cm, with uptake greater than that of mediastinal blood pool (81)
- Participant will undergo a repeat FDG PET/CT scan if the original FDG/PET imaging performed at an outside institution is not of adequate imaging quality for subjects enrolling in the residual FDG mass arm.

4.1.2 Exclusion Criteria

- Known allergy to fluorothymidine
- Participants for whom enrollment would significantly delay (> 2 weeks) the scheduled standard of care therapy.
- Participants with any coexisting medical or psychiatric condition that is likely to interfere with study procedures and/or results are excluded
- Participants with severe claustrophobia not relieved by oral anxiolytic medication or patients weighing >136 kg (weight limit for scanner table)
- Other medical conditions deemed by the PI or associates to make the patient ineligible for protocol procedures.

4.1.3 Research eligibility evaluation (required within 2 weeks of each investigational agent (FLT) injection)

- Liver enzymes: Should be completed within 14 days before injection of the radiopharmaceutical
- SGOT, SGPT <5x ULN
- bilirubin ≤ 2 x ULN
- Negative urine or serum HCG

4.2 Registration Process

4.2.1 NCI Patient Registration

Authorized staff must register an eligible candidate with NCI Central Registration Office (CRO) within 24 hours of signing consent. A registration Eligibility Checklist from the web site (<http://intranet.cancer.gov/ccr/welcome.htm>) must be completed and faxed to [contact]. Verification of Registration will be forwarded electronically via e-mail to the research team. A recorder is available during non-working hours.

4.2.2 Patient Registration for Participating Site:

All patients must be registered through the NCI Central Registration Office (CRO). The CRO is open from 8:30am to 5:30pm EST Monday through Friday, excluding federal holidays. A protocol registration form and cover memo will be supplied by the Coordinating Center, NCI CCR and updates will be provided as needed. Subject eligibility and demographic information is required for registration. To register a subject, send the completed registration checklist to Coordinating Center's Research Nurse, [name] RN, [contact], and [contact]. Please indicate on the protocol registration form whether the patient is screening or is eligible to start treatment. The CRO will notify you either by e-mail or fax that the protocol registration form has been received. The CRO will assign a unique patient/subject

ID number for each subject that will be used to enter data into the C3D data base. Questions about eligibility should be directed to the Coordinating Center's Research Nurse, [name] RN, [contact], and [contact]. Technical questions about the form should be directed to the Central Registration Office [contact]).

5 Study implementation

5.1 Overall Trial Design

A member of the research team will perform the initial eligibility screening.

Informed consent will be obtained prior to the first FLT imaging study. If not obtained within 3 weeks of scheduled FLT imaging, liver enzymes will be drawn.

5.1.1 For subjects enrolling in early response arm

- Participants in this arm will undergo a pre-treatment FLT PET/CT and FDG PET/CT (+/- 2 weeks of each other) imaging prior to beginning lymphoma therapy.
- They will then continue in a lymphoma therapy trial at the NIH Clinical Center or receive a new course of treatment at their home institution.
- Repeat FDG and FLT PET/CT studies will be performed following 2 cycles of chemotherapy.
 - The FDG PET/CT study should be performed as close as possible (i.e. within 4 days) before the subsequent cycle; for example, on days 17 to 21 of a 21-day cycle.
 - The repeat FLT PET/CT imaging should be performed within +/- 2 weeks of the FDG PET/CT study.
- Post treatment FDG and FLT PET/CT studies will be performed
 - The FDG PET/CT study will be performed ≥ 3 weeks after the completion of chemotherapy
 - The FLT PET/CT scan will be performed within +/- one week of the 3rd FDG PET/CT.
- Patients in this arm with residual FDG positive mass following completion of therapy may be enrolled in the residual mass arm.
- The target lesion will be defined as the hypermetabolic (uptake > background) lesion ≥ 1 cm with the highest SUV_{max} at 1 hour post injection
- Primary analyses will be performed on the target lesion and compared with complete response (CR or Cr_u, [Table 6](#)).

5.1.2 For subjects enrolling in the residual mass arm

Patients enrolled in an NIH Clinical Center lymphoma therapy protocol having a residual mass ≥ 1 cm in longest dimension as measured by the CT component of the PET/CT with FDG uptake greater than that of mediastinal blood pool will undergo an FLT PET/CT within 2 weeks of the post treatment FDG PET/CT study. Patients on other lymphoma therapies from outside institutions, must have a FDG PET/CT positive mass ≥ 1 cm, with uptake greater than that of mediastinal blood pool (81). Participant will undergo a repeat FDG PET/CT scan if the original FDG/PET imaging performed at an outside institution is not of "adequate imaging quality" for subjects enrolling in the residual FDG mass. The patient will undergo an FLT PET/CT within 2

weeks of the FDG PET/CT. Patients will undergo clinically indicated biopsy of the residual mass after FLT PET/CT imaging. Fine needle aspiration (FNA) will be performed when biopsy is not possible. If a biopsy is not medically indicated, then the patient will be followed medically by the Lymphoma Team or by their outside oncologist.

The FLT SUV will be compared with pathological response, with the presence of any viable lymphoma cells on biopsy being considered positive for malignancy. For patients who do not undergo biopsy, the absence of tumor will be assessed by lack of lesion progression on routine medical follow-up. An FLT SUV greater than mediastinal background will be considered positive for malignancy.

5.2 [¹⁸F]FLT PET/CT imaging

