- Subjects enrolling in the early response arm must undergo baseline FLT PET prior to receiving a new course of lymphoma therapy.
- Subjects enrolling in the residual mass evaluation arm can be enrolled at the time the FDG avid residual mass is discovered (i.e. no pre-therapy FLT image is required).
- Subjects can enroll in both arms of the study.
- Participant must be 18 years or older.
- ECOG Performance score of 0 or 1
- SGOT, SGPT <5x ULN
- bilirubin \leq 2x ULN

Design:

[figure not shown]
- There are 2 arms in this study
 - The first arm will assess FLT as an early predictor of tumor response to therapy (treatment naive or recurrent disease). Subjects are imaged with FLT and FDG PET pre-therapy, following 2 cycles of therapy and post therapy.
 - The second arm will assess lymphoma patients with FDG PET positive residual mass. Subjects are imaged with FLT PET prior to standard of care biopsy of residual mass. If initial FDG PET data is not available in DICOM format or is of

suboptimal image quality, a repeat FDG PET/CT at the study site may be required.

- We will accrue 70 participants (40 in the early response arm and 30 in the residual mass arm) to this study.

Study Schema

Early response arm

*Complete response as defined by the Cheson revised response criteria and FDG PET/CT Imaging Subcommittee of the International Harmonization Project in Lymphoma

Residual FDG PET positive residual mass arm

[figure not shown]

TABLE of CONTENTS

PRECIS	4
1 INTRODUCTION	8
1.1 Objectives.....	8
1.2 Background	8
1.3 FDG PET for Response Assessment of Lymphoma at the Conclusion of Therapy	9
1.4 FDG PET for Response Assessment of Early Treatment Response.....	10
1.5 FLT scanning for early response to therapy	12
1.6 FLT PET imaging compared with FDG PET imaging	12
1.7 Findings as of March 1, 2013:.....	13
2 Rationale	14
3 Imaging Agent Information	14
3.1 Pharmacology and Toxicology.....	14
3.2 Toxicity of FLT in Humans	14
3.3 Dosimetry.....	15
3.4 Previous human [¹⁸ F]FLT imaging studies	16
3.5 Reported Adverse Events and Potential Risks	20
3.6 [¹⁸ F]FLT Administered Dose	20
3.7 Agent Availability	20
4 Eligibility assessment and enrollment	20
4.1 Eligibility Criteria	20
4.2 Registration Process	21
5 Study implementation	22
5.1 Overall Trial Design.....	22
5.2 [¹⁸ F]FLT PET/CT imaging.....	23
5.3 Pathology (residual mass arm only)	23
5.4 Treatment modifications	24
5.5 Imaging Interpretation.....	24
6 Protocol evaluations.....	26
6.1 Study Calendar	26

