5.3 Pathology (residual mass arm only)

In patients with FDG avid residual masses (uptake greater than mediastinal blood pool) who would routinely undergo biopsy or fine needle aspiration (FNA), the pathology results will be collected and compared with the corresponding FLT SUV. The presence of any viable lymphoma cells will be considered positive for residual malignancy. Biopsy is not medically

indicated in many patients undergoing therapy and therefore, determination of active disease will be based on clinical follow-up in those patients.

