6.1 Study Calendar

Table 5

	Pre-study	Pre-therapy (biopsy for the Residual Mass arm)	Post 2-cycles	End of study
Enroll in CALGB 50303 or other lymphoma therapy trial or undergoing a new course of treatment of lymphoma at another	X			

	Pre-study	Pre-therapy (biopsy for the Residual Mass arm)	Post 2-cycles	End of study
facility				
Informed Consent	X			
Check Liver Function	X	X	X	X
Urine or Serum HCG	X	X	X	X
Early Response Arm				
FDG PET/CT	X	X ^c	X	X
FLT PET/CT		X ^c	X	X ^a
Residual Mass Arm				
FDG PET/CT	X ^b			
FLT PET/CT		X		

^aThe FLT PET/CT scan will be performed at least 12 hours after, and +/- 2 weeks of, the FDG PET/CT study

^bIf not performed at NIH or WRNMMC a repeat FDG PET/CT will be performed according to the prescribed FGD PET/CT protocol within 2 weeks of the FLT PET/CT study

^c Baseline FDG and FLT PETs must be performed prior to initiation of the current/new therapy in patients in the Early Response arm

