6.2 Concurrent Therapies

No restrictions

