7.2.2 Residual Mass arm

The presence of viable lymphoma cells on biopsy/FNA or absence of lesion progression on medical follow-up will be considered positive for residual malignancy.

8 Statistical Section

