8.1.3 Analysis Plan

For the primary analyses, sensitivity and specificity will be estimated and 95% confidence intervals provided. Subjects with an FLT SUV greater than mediastinal blood pool activity will be considered FLT positive. In the early response arm, subjects with complete response (CR or Cr_u, **Table 6**) as determined by the CHESON revised response criteria will be considered disease negative (all others will be considered disease positive). In the residual mass arm, subjects with any malignant cells on biopsy will be considered disease positive.

For secondary objectives 2a and 2d, empirical ROC curves will be estimated, along with non-parametric AUCs and corresponding 95% confidence intervals. For 2b, we will evaluate the ability of FLT to predict clinical response independent of other known predictors using logistic regression. For aim 2c, we will test for differences using signed-rank tests.

No stratification based on lymphoma histology or treatment is planned due to the small amount of expected variability in treatments available.

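### For unbiopsied patients in the residual mass arm, sections 5.1.2 and 7.2.2 define disease status in opposite directions; separately, no limit is set on the FLT-to-biopsy interval

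*Combined protocol and SAP*

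**What the plan says.** **Patients without a biopsy.** The combined protocol and SAP addresses them in four places.

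- Section 5.1.2 judges the absence of tumour by the lesion not progressing on routine follow-up. No progression means disease negative.
- Section 5.3 notes that biopsy is not indicated in many patients and that clinical follow-up then decides active disease. It gives no direction.
- Section 7.2.2, the response criteria for this arm, joins viable cells on biopsy or FNA to a second criterion: "absence of lesion progression on medical follow-up will be considered positive for residual malignancy". No progression means disease positive.
- Section 8.1.3, the analysis plan, says only "In the residual mass arm, subjects with any malignant cells on biopsy will be considered disease positive". It does not mention follow-up.

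**Patients with a biopsy.** Section 5.1.2 says "Patients will undergo clinically indicated biopsy of the residual mass after FLT PET/CT imaging". The Precis, under Design, gives the same order: "Subjects are imaged with FLT PET prior to standard of care biopsy of residual mass". Section 5.3 adds that "the pathology results will be collected and compared with the corresponding FLT SUV". The arm has one stated time window, in 5.1.2 ("The patient will undergo an FLT PET/CT within 2" weeks of the FDG scan), and it links the two scans, not scan and biopsy. The calendar in 6.1 places the FLT scan in a column headed "Pre-therapy (biopsy for the Residual Mass arm)", without days. Section 6.2 on concurrent therapies reads "No restrictions".

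**The concern.** Sensitivity and specificity need one fixed rule for who is diseased. For the unbiopsied part of this arm the plan has two, and they are opposites. An FLT-negative mass that stays stable is a true negative under 5.1.2 and a false negative under 7.2.2. An FLT-positive mass that stays stable is a false positive under 5.1.2 and a true positive under 7.2.2. Because 8.1.3 is silent, an analyst who turns to the response criteria section would take the inverted rule.

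The estimate at stake is a primary one, with about 15 patients expected in each disease group. The plan justifies that size by confidence limits above 50%, so a few misclassified patients matter.

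The secondary concern is that a biopsy taken well after the scan, or after new lymphoma treatment, can describe a different disease state from the one FLT imaged. The error can run either way. A viable mass cleared by treatment before biopsy would look like a false positive scan. A benign mass that relapses and is then sampled would look like a false negative one.

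**Working it through.** **Inputs, all from section 8.1.4:** 30 patients, half with positive pathology, giving 15 positive and 15 negative; anticipated sensitivity 0.85 and specificity 0.90; exact 95% limits; threshold 0.50.

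**Plan's own figures.** The Clopper-Pearson two-sided lower limit is the 0.025 quantile of Beta(x, n − x + 1). For 12/15, 13/15 and 14/15 it gives 0.519, 0.595 and 0.681. Table 8 states 0.52, 0.60 and 0.68, so it reproduces.

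**Effect of 7.2.2 as written.** Let m of the 15 truly negative patients be unbiopsied and non-progressing. Under 5.1.2 they count as negative and nothing changes. Under 7.2.2 they join the positives, and a fraction 1 − 0.90 = 0.10 of them is FLT positive:

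apparent sensitivity = (0.85 × 15 + 0.10 × m) / (15 + m)

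| m (assumed) | Expected sensitivity | Nearest count | Exact lower limit |
|---|---|---|---|
| 0 | 12.75/15 = 0.85 | 13/15 | 0.595 |
| 1 | 12.85/16 = 0.803 | 13/16 | 0.544 |
| 2 | 12.95/17 = 0.762 | 13/17 | 0.501 |
| 3 | 13.05/18 = 0.725 | 13/18 | 0.465 |
| 5 | 13.25/20 = 0.663 | 13/20 | 0.408 |
| 10 | 13.75/25 = 0.550 | 14/25 | 0.349 |

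Expected specificity stays at 0.90 but rests on 15 − m patients. With m = 5 the nearest count is 9/10, with a lower limit of 0.555.

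Section 7.2.2 does not say how an unbiopsied patient who progresses is classed. If it is read as its complement, that patient becomes negative, and specificity suffers as well. The table leaves this out.

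**Biopsy timing (secondary).** If d viable masses are cleared by treatment before biopsy, apparent specificity is (0.90 × 15 + 0.15 × d) / (15 + d). For d = 1, 2, 3 this is 13.65/16 = 0.853, 13.80/17 = 0.812 and 13.95/18 = 0.775. The lower limits at 14/16, 14/17 and 14/18 are 0.617, 0.566 and 0.524. If r benign masses are biopsied only after a later relapse, apparent sensitivity follows the table above with r in place of m: 0.803, 0.762 and 0.725, with lower limits 0.544, 0.501 and 0.465. Of these six limits, five stay above 0.50. The documents give no frequency for either event, so 1 to 3 of 30 is assumed.

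**Would the follow-up rule repair a late biopsy?** Take a late-biopsied patient and classify by 5.1.2 instead. A viable mass cleared by treatment has not progressed, so it is still negative. A benign mass that relapsed has progressed, so it is still positive. Neither label changes, and the follow-up rule has no time limit of its own.

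**The case against.** **On the contradiction.** The wording of 7.2.2 is very probably a drafting slip. Section 5.1.2 states the sensible direction, and a careful analyst would follow it. That bears on what was intended, but it does not remove the conflict: 7.2.2 is the designated criterion for the arm, and 8.1.3 does not choose between the two.

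**On timing.** A reader might infer that the plan in fact scores FLT against disease status at another time, or that it endorses any biopsy, however late and after whatever treatment. The documents do not support that.

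- They present scan and biopsy as one step. The Precis enrols patients when the FDG-avid mass is found and images them before standard biopsy, and the calendar places the FLT scan in a pre-therapy/biopsy column.
- In 8.1.3 the word any qualifies malignant cells, not biopsies.
- The entry in 6.2 reflects an imaging study that does not direct treatment. It is not a rule that a post-treatment biopsy is a valid reference.
- A biopsy months later in a patient under follow-up is a possibility the text leaves open, not one it describes. Prompt biopsies would cause little error.

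What stands is narrower. No section gives a maximum interval or says how a biopsy after new treatment is handled, and the data elements in 7.1 list neither the biopsy date nor treatment after the scan. The exclusion in 4.1.2 for delaying therapy by more than 2 weeks concerns enrolment and does not bound the scan-to-biopsy interval.

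**Conclusion.** The contradiction between 5.1.2 and 7.2.2 is an error in the text of a primary reference standard and should be corrected. Followed literally, 7.2.2 inverts the contribution of every non-progressing unbiopsied patient. Three of 30 are enough to put the expected lower limit for sensitivity below 0.50. This assumes the planned 15/15 split, the anticipated accuracy, and FLT performance that is the same with or without biopsy. The actual number of unbiopsied patients is not given, although 5.3 expects many.

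The missing scan-to-biopsy interval is a lesser point: detail to add, with unknown frequency and a size that rests wholly on assumption. It does not show that the primary estimate is biased.

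**What to change.** **Correct 7.2.2.** Viable lymphoma cells on biopsy or FNA, or lesion progression on follow-up, is positive for residual malignancy; absence of progression is negative. Put the same rule in 8.1.3 so that the analysis plan covers unbiopsied patients. This costs one sentence in each place.

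**Handle timing in the analysis and leave the clinical timing of biopsy as it is.**

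- Record the biopsy date and any lymphoma treatment between scan and biopsy, and report the FLT-to-biopsy interval. These items must be added to the list in 7.1.
- Add a sensitivity analysis that excludes patients biopsied after new lymphoma treatment or outside a window fixed without reference to FLT results. The investigators should choose its length.
- Do not reassign those patients to the follow-up rule. As shown above, that leaves the error in place and gives up histology for a looser reference.

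The costs are two extra data items and a smaller n in the sensitivity analysis. Section 1.7 reports 22 of 30 patients already in this arm and data already reviewed, so the window comes late. The report should say so.
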